All research staff at the MGH Recovery Research Institute are fully trained in relevant ethical principles and procedures, including maintaining confidentiality, and are certified by Collaborative Institutional Training Initiative (CITI) to conduct research with human subjects. During the study, we will notify officials, as mandated by law, if a participant reports intentions to harm himself/herself or others, or reports child or elder abuse. Participants will be informed of these limits to confidentiality during the consenting process. Serious adverse events will be reported to the MGH Institutional Review Board immediately by telephone and by written report within 24 hours of our receipt of information regarding the event.

8. Benefits

A potential participant benefit for the experimental group is improved substance use and affective outcomes. A potential participant benefit for both the experimental and control groups may be increased awareness of personal patterns in affect through the conduct of ecological momentary assessment.

There are also considerable benefits to society associated with this study. Substance problems carry a tremendous emotional, medical, interpersonal, and societal cost. The knowledge gained in this study may lead to the adoption of a novel SUD treatment tool that bridges gaps in existing treatment approaches. The minimal risks associated with this research are reasonable given the potential benefits of this study.

9. Statistical Analysis

Because this is a pilot study with limited power to detect statistical significance, we will focus on interpreting effect sizes to inform a subsequent R01 trial. We note however, certain design strengths that will allow us to maximize statistical power. For instance, in our regression models, rather than just looking at main effects of group, we will also assess Heart Rate Variability Biofeedback (HRVB) practice time as a continuous measure with controls scored as 0. Additionally, power to test day-level associations is boosted by the repeated measures design with up to 84 repeated, momentary assessments per participant.

Please note that we use the term “day-level” below to denote effects at the level of individual ecological momentary assessment (EMA) surveys. From this perspective we have up to 84 repeated, momentary assessments of affect and substance use.

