Using multilevel models where days (L1) are nested within persons (L2), we will explore the effects of day-level HRVB practice earlier in the day (i.e., lagged) on subsequent day-level negative affect (**Model 1**), craving (**Model 2**), positive affect (**Model 3**), and substance use (yes/no; **Model 4**), while also testing whether HRVB decouples the anticipated relationship of day-level negative affect (**Model 5**) and craving on subsequent substance use (**Model 6**).

In models 1-3 (multilevel linear regression models), the dependent variables will be day-level negative affect scores, day-level craving scores, and day-level positive affect scores, with lagged day-level minutes of scheduled practice, and lagged in-the-moment HRVB practice (with controls' HRVB practice coded as 0), and their interaction term (lagged scheduled practice \times lagged in-the-moment practice) as the independent variables, controlling for age, sex, nicotine use (yes/no), medications known to affect the cardiovascular system (yes/no), and baseline past-month AOD use (percent days abstinent).

A priori, we anticipate that both greater daily scheduled HRVB practice and in-the-moment HRVB practice will predict lower subsequent day-level negative affect and craving, and that their interaction will indicate additive benefits of combining scheduled and in-the-moment practice. The relationship between positive affect and HRVB has not previously been explored, so we will treat this aspect of the analysis as exploratory. Our benchmark for preliminary demonstration of treatment benefit will be semi-partial R²'s for practice time of $\geq .10$ (medium effect size).

Models 1-3

Negative affect = day-level scheduled HRVB practice_{t-1} + day-level in-the-moment HRVB practice_{t-1} + [day-level scheduled HRVB practice_{t-1} * day-level in-the-moment HRVB practice_{t-1}] + age + sex + nicotine use + medications known to affect the cardiovascular system + baseline past-month AOD use + error

Craving = day-level scheduled HRVB practice_{t-1} + day-level in-the-moment HRVB practice_{t-1} + [day-level scheduled HRVB practice_{t-1} * day-level in-the-moment HRVB practice_{t-1}] + age + sex + nicotine use + medications

*known to affect the cardiovascular system + baseline past-month AOD use
+ error*

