Positive affect = *day-level scheduled HRVB practice_{t-1} + day-level in-the-moment HRVB practice_{t-1} + [day-level scheduled HRVB practice_{t-1} * day-level in-the-moment HRVB practice_{t-1}] + age + sex + nicotine use + medications known to affect the cardiovascular system + baseline past-month AOD use + error*

In Model 4 (multilevel logistic regression), the dependent variable will be day-level substance use (yes/no), with lagged day-level minutes of scheduled, and lagged day-level minutes of in-the-moment HRVB practice (with controls' HRVB practice coded as 0), and their interaction term (scheduled practice \times in-the-moment practice) as the independent variables, controlling age, sex, nicotine use (yes/no), medications known to affect the cardiovascular system (yes/no), and baseline past-month AOD use (percent days abstinent). We will also test this model with group as independent variable instead of HRVB practice.

In Models 5-6 (multilevel logistic regression), we will use a model building approach, where we will systematically increase model complexity in steps to sequentially examine hypotheses while maintaining a parsimonious model. Likelihood ratio tests will be used to examine the relative fit of nested models (i.e., the difference in -2 log-likelihood statistics between pairs of base and expanded models).

In Model 5, the dependent variable will be day-level substance use (yes/no), with combined lagged day-level scheduled and lagged in-the-moment HRVB practice (with controls' HRVB practice coded as 0), lagged day-level negative affect, and the lagged HRVB practice \times lagged negative affect interaction term as the independent variables, controlling for age, sex, nicotine use (yes/no), medications known to affect the cardiovascular system (yes/no), and baseline past-month AOD use (percent days abstinent). We will also test this model with group as independent variable instead of HRVB practice.

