In Model 6, lagged day-level craving will be added to Model 5. As with the previous model, the dependent variable will be day-level substance use (yes/no), with lagged day-level scheduled and lagged in-the-moment HRVB practice combined (with controls' HRVB practice coded as 0), lagged day-level negative affect, lagged day-level craving, and the lagged HRVB practice \times lagged craving interaction term as the independent variables, controlling for age, sex, nicotine use (yes/no), medications known to affect the cardiovascular system (yes/no), and baseline past-month AOD use (percent days abstinent). We will also test this model with group as independent variable instead of HRVB practice.

We anticipate that greater HRVB practice and lower negative affect and craving will be associated with lower probability of substance use at the subsequent EMA survey, and that the HRVB practice \times negative affect/craving interaction terms will indicate that HRVB practice mitigates the deleterious relationship between negative affect and craving, and subsequent substance use. McFadden's $R^2 \geq .10$ (medium effect size) will be our benchmark for preliminary demonstration of day-level treatment benefit.

Models 4-6

Substance use = *day-level scheduled HRVB practice_{t-1} + day-level in-the-moment HRVB practice_{t-1} + [day-level scheduled HRVB practice_{t-1} * day-*

level in-the-moment HRVB practice_{t-1}] + age + sex + nicotine use + medications known to affect the cardiovascular system + baseline past-month AOD use + error

Substance use = *total day-level HRVB practice_{t-1} + day-level negative affect_{t-1} + [total day-level HRVB practice_{t-1} * day-level negative affect_{t-1}] + age + sex + nicotine use + medications known to affect the cardiovascular system + baseline past-month AOD use + error*

Substance use = *total day-level HRVB practice_{t-1} + day-level negative affect_{t-1} + day-level craving_{t-1} + [total day-level HRVB practice_{t-1} * day-level negative affect_{t-1}] + [total day-level HRVB practice_{t-1} * day-level craving_{t-1}] + age + sex + nicotine use + medications known to affect the cardiovascular system + baseline past-month AOD use + error*

Aim 2a Power

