With $N= 100$, and 42 days of EMA monitoring with 2 self-reports per day, the multilevel models exploring day-level relationships between HRVB practice, affect, and substance use will include 8,300 clustered observations. Given 5% alpha and a substance use/HRVB practice association of $r= 0.15$, and assuming conditional independence, we will have >99% power to predict a main effect of HRVB practice in Models 1-6.

Aim 2b. Test the accumulative, person-level effects of scheduled daily HRVB practice vs. in-the-moment HRVB practice, vs. their interaction on substance use during the 8-week intervention period

To begin to tease out the aggregated effects of scheduled vs. in-the-moment HRVB practice on substance use, we will run a linear regression model with percent days abstinent (PDA) from alcohol and other drugs (AOD) over the 8-week study period as the dependent variable, with total aggregated scheduled HRVB practice time, total aggregated in-the-moment HRVB practice time, and their interaction term (scheduled practice \times in-the-moment practice) as independent variables (with controls' HRVB practice coded as 0), controlling for age, sex, nicotine use (yes/no), medications known to affect the cardiovascular system (yes/no), and baseline past-month AOD use (percent days abstinent; **Model 7**). We will also run versions of this model testing a main effect of group, and number of in-the-moment practice sessions rather than aggregated in-the-moment HRVB practice time.

A priori, we anticipate that both greater accumulative scheduled HRVB practice, and accumulative in-the-moment HRVB practice will predict greater PDA, and importantly, that their interaction will indicate additional benefits of combining scheduled and in-the-moment practice. A semi-partial R^2 value for HRVB practice time $\geq .10$ (medium effect size) will be our benchmark for preliminary demonstration of aggregate-level treatment benefit.

An ancillary aim of this study is to explore the effects of differing HRVB practice times on treatment outcomes. We will conduct a post hoc regions-of-significance analysis to explore the moderation effect of practice time on the relationship between PDA and HRVB practice. This analysis will consider the effect for several alternate cutoff scores representing the 10th, 20th, 30th, 40th and 50th percentiles of practice time.

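### The treatment-benefit benchmark for Models 4–6 is a whole-model McFadden R², so in Models 5–6 strong affect and craving effects can meet it when HRVB does nothing or harm

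*Combined protocol and SAP*

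**What the plan says.** Section 9 sets three benchmarks for a preliminary showing of benefit.

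- **Models 1–3 (Aim 2a, affect and craving outcomes):** "Our benchmark for preliminary demonstration of treatment benefit will be semi-partial" R² for practice time, at least .10.
- **Model 7 (Aim 2b, percent days abstinent):** a semi-partial R² for HRVB practice time of at least .10 "will be our benchmark for preliminary demonstration of aggregate-level treatment benefit".
- **Models 4–6 (Aim 2a, substance use yes/no):** McFadden's R² of at least .10 "will be our benchmark for preliminary demonstration of day-level treatment benefit". No terms, null model or sign are specified.

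Model 4 contains the two practice variables, their interaction and five covariates. Model 5 replaces these practice terms with total practice and adds lagged negative affect and its interaction with practice. Model 6 adds lagged craving. The plan expects that "lower negative affect and craving will be associated with lower probability of substance use at the subsequent EMA survey". For Models 5–6 it also says that "Likelihood ratio tests will be used to examine the relative fit of nested models". The opening of Section 9 states that the pilot will "focus on interpreting effect sizes to inform a subsequent R01 trial".

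**The concern.** The first two benchmarks credit only what practice time explains. The third credits everything in the model. Models 5–6 include predictors that the authors themselves expect to work, and the fit those predictors produce would count as HRVB benefit. Because the statistic has no sign, an HRVB effect that makes use more likely also raises it.

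The pilot's stated product is effect sizes for a later trial. A Model 6 result reported as meeting the treatment-benefit benchmark could therefore carry into that trial's rationale without any HRVB effect behind it. The reverse error is also possible: a helpful HRVB effect can miss the benchmark when affect and craving explain little.

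**Working it through.** **The plan's own figure.** Aim 2a Power: "Given 5% alpha and a substance use/HRVB practice association of" r = 0.15, with 8,300 observations, gives power above 99%. By Fisher's z, atanh(.15) × √(8,300 − 3) − 1.96 = .1511 × 91.09 − 1.96 = 11.8, so power exceeds .999 under the plan's assumption of conditional independence. The figure reproduces. (100 people × 83 lagged surveys = 8,300, since the first of 84 has no predecessor.) The .10 benchmark is a chosen threshold and has no derivation to reproduce.

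**Definitions.**
- Standard McFadden R² = 1 − lnL(model) / lnL(null).
- HRVB increment = [lnL(model) − lnL(same model without HRVB terms)] / |lnL(null)|.

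**Inputs from the documents.** 100 people, 83 lagged surveys, 70:50 allocation (58% HRVB), controls' practice coded 0, and the predictors of Models 4–6.

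**Assumed inputs (not in the documents).** Use at 7.5% of surveys, random-intercept SD 1.0 or 1.5, 60% of affect variance within person, affect–craving correlation about .5, and the odds ratios below. The correlation is not extreme. The negative-affect index includes craving as one of five items, so even uncorrelated items of equal variance would give 1/√5 = .45.

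**Random-intercept logistic model, true HRVB effect zero, random-intercept null, 20 runs per setting.** Mean R² at SD 1.0 / 1.5:

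| Odds ratio per SD: affect, craving, baseline percent days abstinent (PDA) | Model 5 | Model 6 | Model 6 reaches .10 |
|---|---|---|---|
| 1.5, 1.5, .7 | .037 / .032 | .047 / .042 | 0% of runs |
| 1.8, 1.5, .6 | .054 / .052 | .064 / .063 | 0% |
| 2.0, 2.0, .5 | .085 / .081 | .114 / .108 | 90–100% |
| 2.5, 2.0, .5 | .117 / .112 | .144 / .140 | 100% |

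- Model 4 is .004–.008 and never meets the benchmark.
- The mean HRVB increment is .0004–.0016; the largest in any run is .0047.
- At 2.0/2.0/.5 and SD 1.0, Model 6 is .114 with 3% use (met in 90%) and .120 with 15% use (100%).
- **Harmful HRVB, odds ratio 1.2 per SD, affect and craving 2.0:** Model 6 is .114–.115, met in 85–100% of runs. The HRVB terms contribute only .004–.005.
- **Where the threshold is crossed:** with affect and craving both 1.8 and PDA .6, Model 6 is .080–.088 (met in 0–17% of 12 runs). With both 2.0, no PDA effect and SD 1.5, it is .102 (67% of 12 runs).

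**Simpler check: single-level logistic fits, use 5–20%, HRVB effect zero.** With affect and craving both 2.0, Model 5 is .114–.123 (met in 90–100%) and Model 6 is .155–.171 (100%), with an HRVB increment of at most .0012. At 1.5 neither model meets .10. Conversely, a beneficial HRVB odds ratio of 0.5 per 7.5 minutes with no affect or craving effect gives an R² of only about .02 (5–10% use), a miss.

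**Null model.** It is unstated, and the choice matters. Against a single-level null, a random intercept with no predictors already scores .10–.21. Nothing in the plan says that null would be used, so the conclusion does not rest on this.

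**What .10 means as an increment.** For one predictor, R² ≈ r² / (2H), where H = −p ln p − (1 − p) ln(1 − p) and p is the use rate. With r = .15, r² = .0225:

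| p | H | .0225 / (2H) |
|---|---|---|
| 5% | .1985 | .057 |
| 10% | .3251 | .035 |
| 20% | .5004 | .022 |
| 50% | .6931 | .016 |

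Exact values for a normal predictor agree (.057, .035, .023, .016). An increment of .10 needs r of about .20 at 5% use and .36 at 50%. So the effect assumed for power would miss a .10 increment at all these rates.

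**The case against.** **An increment may have been meant.** The other two benchmarks are HRVB-specific and the three sentences run in parallel, so loose drafting is plausible. The likelihood ratio tests could supply an increment. But they are described only for Models 5–6, are not tied to the benchmark, and no text says that the base model omits HRVB. If an increment was meant, the plan should say so.

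**A null or harmful effect would be seen.** The sentence before the benchmark gives the expected direction, Models 4–6 are refitted with group in place of practice, and coefficients would presumably be reported. This lowers the risk of a misleading report but does not change the criterion. The semi-partial R² of the other models also has no sign, so the lack of direction is not peculiar to McFadden's statistic. The crediting of non-HRVB terms is.

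**The effects needed are strong.** This stands. The threshold is crossed only near odds ratios of 2.0 for both predictors, mutually adjusted. With correlation .5 that equals exp(ln 2 × √3) = 3.3 per SD of their sum. The main 2.0 scenario also assumes a baseline-PDA odds ratio of .5. In the random-intercept model, Model 5 passes on average only at an affect odds ratio of 2.5.

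**Model 4 is barely affected.** This stands. Only its covariates could lift it: a baseline-use odds ratio of 2.5 per SD gave .100–.107 in single-level fits.

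**It is a pilot with no go/no-go rule.** True, and it limits the severity. But effect sizes are what the pilot is meant to deliver.

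**Conclusion.** The concern holds, chiefly for Model 6 and to a lesser degree for Model 5. As written, the criterion can label fit from affect and craving as HRVB benefit, and no other text in the plan corrects this. Under the assumed inputs, with affect and craving odds ratios near 2.0 per SD, a null HRVB effect meets the Model 6 benchmark in most or all runs while contributing .002 or less on average. A modestly harmful effect meets it too. At odds ratios of 1.5–1.8 for affect and 1.5 for craving, the problem does not appear. The wording defect does not depend on these inputs; how often it would mislead does. It should be fixed before analysis.

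**What to change.** 1. Define the benchmark for each of Models 4–6 as the McFadden increment from the HRVB (or group) terms and their interactions: the log-likelihood with those terms minus the log-likelihood without them, divided by the absolute log-likelihood of a random-intercept null. Use the same random effects and the same observations in all three fits.
2. State that the base model without HRVB terms is fitted for each of Models 4–6.
3. Require the beneficial direction and report the odds ratio with its 95% CI. Centre affect and craving so that the HRVB coefficient in Models 5–6 is the effect at their mean. For Model 4, which has two practice terms and their interaction, state the practice contrast at which direction is judged.
4. Re-justify or restate the .10 cut-off for this increment, since the r = .15 used for power gives about .06 at 5% use and .016 at 50%.

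The cost is a few sentences in the analysis section and one extra fit per model, with no new data. The benchmark becomes harder to meet, so item 4 has to be settled at the same time as item 1.
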